**EFFICACY OF CONTINUOUS GLUCOSE MONITORING IN NEONATAL HYPOGLYCEMIA*****Project Summary:***

*We aim to evaluate the utility of continuous glucose monitors (CGMs) in improving the diagnosis and management of neonatal hypoglycemia in infants admitted to the neonatal intensive care unit (NICU). Specifically, we hope to assess whether the use of CGMs in this population reduces the number of hypoglycemic events, reduces the time to diagnosis of the etiology of hypoglycemia and/or reduces the time taken to achieve stable euglycemia on a sustainable feeding regimen. We plan to perform a prospective randomized controlled pilot study comparing the clinical course and outcomes of newborns with hypoglycemia admitted to the NICU who are actively monitored with CGMs versus those who receive routine care.*

**1. Specific Aims and Objectives**

We seek to improve the management and outcome of neonates diagnosed with hypoglycemia. We hope to accomplish this by using continuous glucose monitors (CGMs) in at-risk infants admitted to the neonatal intensive care unit (NICU). Current management of neonatal hypoglycemia involves intermittent blood sampling, which, unlike CGMs, does not offer real-time blood glucose trends and therefore leaves infants at risk for unrecognized hypoglycemia. Unrecognized hypoglycemia may not only lengthen time to diagnosis and appropriate treatment, but may also lead to poor neurodevelopmental outcomes. Our long-term goal is to assess whether use of CGMs can improve clinical course and outcomes in this population. This pilot study will allow us to test whether it is feasible to perform in larger-scale the proposed randomized, controlled trial comparing a “CGM Protocol” group and a “Standard of Care” group to assess whether use of CGMs in neonates can:

**a) Reduce the number and severity of hypoglycemic events**

*Hypothesis: Use of CGMs will provide real-time blood glucose trends, allowing hypoglycemia to be predicted and prevented, or detected and treated before becoming severe or symptomatic.*

**b) Reduce the time to diagnosis of the etiology of hypoglycemia**

*Hypothesis: Earlier recognition of hypoglycemia with CGMs will prompt earlier testing to evaluate the etiology of the hypoglycemia and therefore lead to earlier ascertainment of the underlying etiology.*

**c) Reduce the time taken to achieve stable euglycemia on a sustainable feeding regimen.**

*Hypothesis: CGMs will shorten time to achieving a stable, normal blood glucose concentration on a sustainable feeding regimen.*

By performing a pilot study we hope to test the feasibility of our study design. We plan to use the results to assess the validity of our chosen outcome measures, inform power and sample size considerations and test the practicality of our study timeline for larger-scale study on the same topic. The results of this study could potentially alter the way neonatal hypoglycemia is routinely managed and thereby improve neurodevelopmental outcomes in this population.

**2. Background and Significance**

Neonatal hypoglycemia affects approximately 10% of all newborns, and up to 50% of infants with risk factors such as maternal diabetes, small for gestational age (SGA; <2500g), large for gestational age

(>4000g), birth at <37 weeks gestational age, and maternal beta blocker or terbutaline therapy 48 hours prior to delivery (1,2). Timely detection and treatment of neonatal hypoglycemia are critical, as failure to do so is associated with poor long-term neurodevelopmental outcomes (3,4). Neonates with symptomatic hypoglycemia are at risk for learning disabilities, seizure disorders, mental retardation and cerebral palsy (5). SGA infants with recurrent hypoglycemia, for example, have been reported to have smaller head circumference at 18 months and lower scores on psychometric tests at 5 years (4). Infants of diabetic mothers with resultant neonatal hypoglycemia have been found to have higher incidence of attention deficits, motor control dysfunction and perception deficiencies (6). Persistent hypoglycemia, often associated with serious metabolic conditions such as hyperinsulinism and fatty acid oxidation defects, is also associated with worse neurological outcomes (7).

Part of the challenge in managing neonatal hypoglycemia is that signs and symptoms can be nonspecific or absent. Clinical signs of hypoglycemia include irritability, poor feeding, tremulousness, and somnolence, all of which can be subtle or mistaken for normal neonatal behavior. The more severe signs, such as seizure, hypothermia, respiratory depression, and coma usually do not present until hypoglycemia has been severe or prolonged (5).

NICU practice guidelines for hypoglycemia monitoring vary from institution to institution. Often, blood glucose testing is done only prior to feeds, which leaves these infants vulnerable to undetected hypoglycemia. Even with frequent blood sampling using bedside glucometers there can be a delay in recognition and treatment of hypoglycemia. CGMs measure glucose concentration in the interstitial fluid of the subcutaneous space every few seconds and report average blood glucose levels approximately every 5 minutes. CGMs have 3 components: a glucose sensor, a transmitter, and a receiver. The glucose sensor is inserted subcutaneously with a 26-gauge introducer needle and remains in place under the surface of the skin for up to 7 days. The sensor's platinum tip is embedded with glucose oxidase enzyme, which catalyzed a reaction whereby electrical current is generated which is proportional to ambient glucose concentration. The current is then measured and translated into a glucose reading once it is wirelessly sent by the transmitter to the small hand-held receiver. The receiver then displays the glucose level in mg/dL and can alert at specified glucose levels. CGMs are inserted with minimal discomfort and no significant complications have been reported when they are used in children less than 3 years of age (8). CGMs are considered by IRBs to be non-significant-risk devices because they are not considered implants, they are placed only subcutaneously, they are completely removed within 7 days, and they do not offer treatment for or diagnosis of a medical condition. In our study, no clinical decision or intervention will be made based on the CGM readings. Instead, the CGMs will function as monitoring systems that will prompt FDA-approved glucose meter measurements, and only on these blood-based results will clinical care be based.

Although CGMs are increasingly being used in the diabetic population, their efficacy has not been investigated in the management of neonatal hypoglycemia. However, their use in the neonatal population, including in very-low-birth-weight infants, has been validated. Studies report that the sensor is well tolerated and provides readings comparable to those of whole blood results (9). It has also been shown that currently in a typical NICU, there are often prolonged periods (up to 12 hours) between blood glucose measurements, and that with CGMs, hypoglycemia is detected up to 3 hours prior to the scheduled blood glucose test (9).

We plan to explore the utility of CGMs in a new clinical context with the hope that they will improve the diagnosis and management of neonatal hypoglycemia. We will compare in a systematic way the clinical course and outcomes of newborns with hypoglycemia admitted to the NICU who are actively monitored with CGMs versus those who receive routine care. As of today, this comparison has yet to be made. The results of this study could potentially alter the way neonatal hypoglycemia is routinely managed and thereby improve outcomes in this population.

### 3. Preliminary Studies

The Safe Pediatric Euglycemia in Cardiac Surgery (SPECS) trial was performed by members of this research team at Boston Children's Hospital. In that study critically ill children undergoing heart surgery were randomized to a control group or a treatment group in which insulin was used to treat maintain euglycemia. All patients in this study were monitored with CGMs. Close to 1,000 children less than 36 months old had CGMs inserted and no injuries, serious bleeding, or infections were reported (10). Moreover, use of CGMs allowed reduction of severe hypoglycemia for patients undergoing tight glycemic control (11).

### 4. Design and Methods

#### a. Study Design

We aim to carry out a prospective, randomized clinical study examining the efficacy of continuous glucose monitoring in neonates with hypoglycemia. Eligible infants will be late preterm and term infants admitted to the Boston Children's Hospital NICU, who have had two documented hypoglycemic episodes during their admission. Hypoglycemia will be defined depending on age: <50 mg/dL prior to 48 hours of life and <70 mg/dL after 48 hours of life.

The research team will review the glucose levels for patients admitted to the NICU daily in order to identify those with hypoglycemia. Screening will be conducted by study staff through the electronic medical record system; supplemental screening will be provided daily through BCH360. After obtaining permission and an introduction from the patient's NICU staff, a member of the research team will contact the family to obtain consent. The goal will be for patients to be recruited within 24 hours after criteria for hypoglycemia have been met.

All enrolled infants will be placed on a CGM monitor (Dexcom G4 Platinum Pediatric Continuous Glucose Monitoring System). The CGM sensor will be inserted subcutaneously in the lateral thigh by a trained study team member. Prior to study commencement, as well as actively throughout the study duration, the research team will review the proper use of CGMs with the NICU staff (most importantly, how to calibrate the sensor with glucose levels from blood sampling). The NICU staff will also be trained to avoid using sensor values to guide treatment directly, as it is only a monitoring device. All concerning CGM glucose readings must be confirmed by blood glucose sampling.

Infants will be randomized to a "CGM Protocol" or a "Standard of Care" group. We aim to enroll ten patients in each study arm. Those on the CGM Protocol will have a fully accessible CGM that will be analyzed in real-time for blood glucose trends and will alarm for any blood glucose level approaching hypoglycemic threshold. The CGM alarm will sound if blood glucose is less than 60 mg/dL for all patients. The CGM will also alarm if the rate of drop in blood glucose is greater than 20 mg/dL/minute and thus concerning for impending hypoglycemia. These thresholds are programmed into the CGM by a study team member and will not be modifiable by the medical team. Those in the "Standard of Care" group will have a CGM in place but live readings will not be available to the clinical team. However, the research team will review CGM data from the "Standard of Care" group daily and if a subject in the "Standard of Care" group has three episodes of unrecognized severe hypoglycemia (eg. BG <40 mg/dL), the study team will alert the NICU providers. Notification will occur immediately following identification of the third unrecognized severe episode of hypoglycemia, which will at most be 24 hours after the event occurred.

For subjects in the "CGM Protocol" group, whenever the CGM alarms or there is a concerning blood glucose trend according to the CGM, the nurse will be asked to check a blood glucose value. All clinical

management decisions will be made by the clinical team based on laboratory or bedside monitor-confirmed blood glucose values. The CGMs will be calibrated, at a minimum, every 12 hours with a blood glucose value measured by bedside glucometer. Additional calibrations will be performed if more frequent blood glucose monitoring is deemed necessary by the NICU team. In the “Standard of Care” group, the only change to current management is the potential performance of additional blood glucose checks that may be prompted if repeated unrecognized severe hypoglycemia is detected by the research team. The CGM will remain in place until the infant is no longer being monitored for glycemic stability or until the infant is discharged. If hypoglycemia work-up and management lasts longer than a week, the CGM sensor will be replaced on the seventh day after initial insertion. In the case of a sensor dislodgement or malfunction, it would also be replaced. Lastly, if a patient continues to have unstable hypoglycemia for longer than 28 days (eg. four 7-day cycles of CGM) then their study participation will also end at that time.

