- *Assessments:*

The CGM site will be evaluated daily to assess for any signs of bleeding or infection. CGM readings will be downloaded to a study team computer once a day. The CGM data will be reviewed daily to ensure the CGM monitor is functioning properly, being calibrated appropriately and to assess whether any episodes of severe unrecognized hypoglycemia have occurred.

- *Interventions:*

Subjects in the study will have a continuous glucose monitor (CGM) placed in one of their thighs. A numbing cream will be used before the CGM is inserted to reduce pain. The CGM has a small plastic catheter with a needle in it. It comes with an insertion device which pushes the catheter under the skin. The needle is then removed, so only the catheter stays under the skin with the device on top of it. After the CGM is placed, two blood glucose levels will be obtained (usually by heel prick) so that the device can be calibrated. Afterwards at least two blood sugar levels need to be obtained every day so that the CGM can continue to work properly. Infants with hypoglycemia need to have their blood glucose monitored routinely, so on most days no extra blood glucose sampling will be required as we will use the values obtained by the NICU team. Additional blood glucose levels may need to be obtained if the CGM reports current or impending hypoglycemia. All non-CGM monitoring and management decisions will be at the discretion of the NICU team. The CGM may need to be replaced in case of a sensor dislodgement or malfunction, or if it has been in place for more than 7 days. Live CGM glucose values will be available to the medical team in the “CGM protocol” group. Additionally the medical team will be provided print outs of the CGM data on a daily basis for the “CGM protocol” group. CGM data from patients in the “Standard of Care” group will also be reviewed daily. Notification will occur immediately following identification of three unrecognized severe episodes of hypoglycemia. Given that the CGM data will be analyzed daily, this will at most be 24 hours (although most likely less than 24 hours) after the event occurred.

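### The rate-of-fall alarm is written as more than 20 mg/dL/minute, a value or unit that is implausible for warning of impending hypoglycemia

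*Combined protocol and SAP*

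**What the plan says.** Section 4a (Study Design) says that the monitor in the CGM Protocol arm "will alarm for any blood glucose level approaching hypoglycemic threshold". Two settings carry this out. One is a fixed level: "The CGM alarm will sound if blood glucose is less than 60 mg/dL for all patients". The other is a rate of fall: "The CGM will also alarm if the rate of drop in blood glucose is greater than 20 mg/dL/minute and thus concerning for impending hypoglycemia". Both are set by the study: "These thresholds are programmed into the CGM by a study team member and will not be modifiable by the medical team".

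The limits that the alarms serve are in the same section: "<50 mg/dL prior to 48 hours of life and <70 mg/dL after 48 hours of life". Section 8 (Data Analysis Plan) puts severe hypoglycemia below 40 mg/dL. Section 2, and again the description of study treatments, say that the monitors "report average blood glucose levels approximately every 5 minutes".

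The alarms are not the only route to a blood test. Section 4a adds that "whenever the CGM alarms or there is a concerning blood glucose trend according to the CGM, the nurse will be asked to check" the level in a blood sample. The interventions part of section 4d says: "Additional blood glucose levels may need to be obtained if the CGM reports current or impending hypoglycemia".

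The rate figure appears once. No rationale, source or alternative unit is given anywhere in the document.

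**The concern.** An alarm for impending hypoglycemia has to respond to falls that are slow enough for glucose still to be above the limit when it sounds. A trigger of more than 100 mg/dL per report is larger than either hypoglycemia limit itself, which points to a slip in the value or the unit.

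Aim (a) in section 1 rests partly on hypoglycemia being predicted and prevented, and the primary endpoint is its incidence and severity. If the written setting were programmed, the automatic predictive part of the intervention would seldom contribute unless glucose started high. If something else were programmed, the protocol would misdescribe the intervention that the pilot is meant to carry into a larger trial.

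**Working it through.** **Inputs.** Rate trigger: more than 20 mg/dL/minute (section 4a). Fixed alarm: below 60 mg/dL (section 4a). Limits: 50 and 70 mg/dL (section 4a); severe, 40 mg/dL (section 8). Reporting interval: about 5 minutes (section 2). The protocol gives no derivation of the trigger, so there is no calculation of its own to reproduce.

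**Step 1. Fall per report.** Rate x interval = 20 x 5 = 100 mg/dL.

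**Step 2. Starting reading needed.** The algorithm is not described. Assume that the rate is judged between consecutive reports. The alarm then fires only if the starting reading exceeds the next reading by more than 100 mg/dL, so the start must be above (next reading + 100). For comparison, the last column assumes a 1-minute window, where the required fall is 20 x 1 = 20 mg/dL. That window fits poorly with 5-minute reporting and is shown only as the favorable extreme.

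| What the alarm should achieve | Next reading at least | Start, consecutive reports | Start, 1-minute window |
|---|---|---|---|
| Fire at all | 0 | above 0 + 100 = 100 | above 0 + 20 = 20 |
| Fire while the <60 alarm is silent | 60 | above 60 + 100 = 160 | above 60 + 20 = 80 |
| Fire with glucose at or above 70 | 70 | above 70 + 100 = 170 | above 70 + 20 = 90 |

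**Step 3. Time available at the written rate.** Minutes to a limit = (start - limit) / 20. The protocol gives no typical starting glucose; 100 mg/dL is assumed.

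- To 70: 30/20 = 1.5 minutes
- To 60: 40/20 = 2 minutes
- To 50: 50/20 = 2.5 minutes
- To 40: 60/20 = 3 minutes

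All of these are shorter than one reporting interval. The result depends on the start: from 200 mg/dL, reaching 70 takes 130/20 = 6.5 minutes, longer than one interval.

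**Step 4. Slower falls.** A steady fall from 100 to 60 mg/dL has a rate of 40 / minutes taken:

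- Over 10 minutes: 40/10 = 4 mg/dL/minute, one fifth of the trigger
- Over 30 minutes: 40/30 = 1.33 mg/dL/minute
- Over 60 minutes: 40/60 = 0.67 mg/dL/minute

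None of these triggers the alarm, whatever window the receiver uses.

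**The case against.** The strongest reply is that the alarm is not useless and that prediction does not hang on it. Much of this stands.

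- **The alarm can still warn.** A reader might infer that it can never sound before a limit is crossed. The documents do not support that: between consecutive reports it can sound at or above 70 from a start above 170 mg/dL. The glucose range in these infants is not given. Section 4d lists intravenous glucose and glucagon among the data to be recorded, so high readings cannot be excluded.
- **Other routes to early warning exist.** Staff in the CGM Protocol arm see live values and daily printouts, and nurses are asked to act on a worrying trend without any alarm. The fixed alarm leads the 50 limit by 10 mg/dL and the severe limit of 40 by 20 mg/dL. It is therefore too strong to say that the predictive part of aim (a) is lost.
- **The setting is not beyond correction.** The medical team cannot change it, but the study team programs it and reviews the CGM data daily. That review does not expressly cover alarm settings.
- **The written figure is not evidence of what was programmed.** A reader might infer that infants were monitored with an ineffective alarm. The document shows only the instruction.

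It is also fair to say that no endpoint, analysis or sample size changes, and that treatment decisions rest on blood values alone. What does not stand is the suggestion that trend checks make the figure harmless. They are left to judgment, whereas this is a programming instruction with a stated purpose that its value does not fit.

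**Conclusion.** The figure is wrong as written, of minor to moderate severity. A trigger of more than 100 mg/dL per report is implausible for an alarm meant to signal approach to 50 or 70 mg/dL. It can warn ahead of those limits only from high starting values: above 170 mg/dL for the 70 limit, and above 160 before it adds anything to the fixed alarm.

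The 160 and 170 figures assume comparison of consecutive reports; the times in Step 3 assume a start of 100 mg/dL. That a steady fall of 4 mg/dL/minute goes unalarmed depends on neither. That the value or unit is a slip is an inference, and the documents do not reveal the intended number. They also do not say how fast glucose falls in these infants, so the amount of warning lost cannot be quantified.

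One neighboring matter should be kept apart. After 48 hours of life the fixed alarm sounds below 60 while the limit is 70, so slow drift into 60-69 mg/dL sounds no level alarm. That comes from the fixed setting, not from this figure.

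**What to change.** Before enrolment, correct the value or unit of the rate alarm in section 4a to a rate that the device supports and the clinical investigators choose. Then check the programmed setting on each receiver and record it.

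Low single digits of mg/dL/minute would be consistent with the stated purpose. As an illustration only, take a fall at the rate shown that is recognized after one 5-minute report. The time left before 70 mg/dL is (start - 70)/rate - 5:

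| Rate (mg/dL/minute) | Fall per report (mg/dL) | From 100 | From 90 |
|---|---|---|---|
| 2 | 2 x 5 = 10 | 30/2 - 5 = 10 min | 20/2 - 5 = 5 min |
| 3 | 3 x 5 = 15 | 30/3 - 5 = 5 min | 20/3 - 5 = 1.7 min |
| 4 | 4 x 5 = 20 | 30/4 - 5 = 2.5 min | 20/4 - 5 = 0 min |

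From 80 mg/dL none of these rates leaves any time (10/2 - 5 = 0 at best), so the gain is real but modest, and the correction does not address slow drift into 60-69 mg/dL.

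The cost is one corrected figure, one recorded device check, and some additional confirmatory blood tests prompted by an alarm that responds to ordinary falls.

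### The masked-arm safety alert counts episodes only, so one prolonged unrecognized CGM low under 40 mg/dL, seen at the daily review, requires no notification

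*Combined protocol and SAP*

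**What the plan says.** All enrolled infants wear a CGM. In the Standard of Care arm, Section 4a states that "live readings will not be available to the clinical team". The research team reviews these masked data daily. If an infant "has three episodes of unrecognized severe hypoglycemia (eg. BG <40 mg/dL), the study team will alert the NICU providers", and the delay after the third event is to be no more than 24 hours. Section 4d (Interventions) repeats the count: "Notification will occur immediately following identification of three unrecognized severe episodes of hypoglycemia".

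Section 4a also says that the only departure from current management in this arm is extra blood checks that "may be prompted if repeated unrecognized severe hypoglycemia is detected by the research team". Section 4d (Assessments) gives the daily review a wider purpose, "to assess whether any episodes of severe unrecognized hypoglycemia have occurred", but attaches no action to a first or second episode.

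Section 4a sets a floor on blood sampling: "The CGMs will be calibrated, at a minimum, every 12 hours with a blood glucose value measured by bedside glucometer". Section 8 defines severe hypoglycemia as below 40 mg/dL. For analysis, a CGM-only event needs more than 30 minutes below threshold, and episodes within one hour of each other are merged. No section says whether those two analysis rules apply to the alert.

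**The concern.** The rule responds to how often severe lows recur and not to how long one lasts. Section 2 says that the gravest signs usually appear only once hypoglycemia has been severe or prolonged, so by the protocol's own account duration matters. It also says that signs can be vague or missing, so bedside observation cannot be relied on to prompt a blood check. It adds that in a typical NICU "there are often prolonged periods (up to 12 hours) between blood glucose measurements", which makes delayed recognition plausible.

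At stake is a situation in which study staff hold a trace showing a long severe low and the protocol does not oblige them to tell the clinicians responsible for the infant. The alert is retrospective and cannot end the low that triggers it. Its value is in prompting checks that guard against a recurrence, and that reasoning applies to one long low as well as to three short ones.

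**Working it through.** The plan states no figure to reproduce. The check is to apply the alert rule to example traces and then look for any other provision that would cover the gap.

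**Inputs**
- Trigger: three unrecognized episodes below 40 mg/dL, no duration (Sections 4a and 4d).
- Reading interval: about 5 minutes (Section 2), so readings = minutes / 5.
- Blood check at least every 12 hours (Section 4a).
- Analysis rules: more than 30 minutes below threshold, one-hour merge (Section 8). Whether they govern the alert is not stated, so both readings are shown.
- Added trigger: one stretch longer than L with no blood value during it, L = 60 or 120 minutes (assumed).

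**Upper bound on one unrecognized low.** 12 × 60 − 5 = 715 minutes, and 715 / 5 = 143 readings. The low must begin just after one blood check and end just before the next.

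**Rule applied to illustrative traces.** All are below 40 mg/dL and unrecognized. The lengths are chosen for illustration and are not rates from the documents.

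| Trace | Minutes | Readings | Current rule, no floor or merge | Current rule, Section 8 floor and merge | Added trigger alone, L = 60 | Added trigger alone, L = 120 |
|---|---|---|---|---|---|---|
| Three of 15 min, over 1 h apart | 45 | 9 | alert | none | none | none |
| Three of 35 min, 65 min apart | 105 | 21 | alert | alert | none | none |
| Three of 35 min, 45 min apart | 105 | 21 | alert | none (merged to one) | none | none |
| Two of 50 min | 100 | 20 | none | none | none | none |
| One of 55 min | 55 | 11 | none | none | none | none |
| One of 115 min | 115 | 23 | none | none | alert | none |
| One of 360 min | 360 | 72 | none | none | alert | alert |
| Two of 360 min, 2 h apart | 720 | 144 | none | none | alert | alert |
| One of 715 min | 715 | 143 | none | none | alert | alert |

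A single unbroken low never meets the current rule under either reading. Joining the added trigger to the current rule by OR cannot remove an alert that the current rule gives.

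**Exposure relative to an alerting pattern.** This depends on the reading. Against three 15-minute lows (no floor): 360 / 45 = 8.0 and 715 / 45 = 15.9. Against three 35-minute lows (floor applied): 360 / 105 = 3.4 and 715 / 105 = 6.8. The finding does not depend on these ratios.

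**Other provisions**
- Section 4a says "All concerning CGM glucose readings must be confirmed by blood glucose sampling". The sentence follows the text on training NICU staff, who have no live readings in this arm. It does not oblige the research team to report a single masked episode.
- Section 5 has the investigator monitor individual data daily, and Section 7 allows a child to be taken off study in the child's best interest. Both are discretionary.
- The 30-minute criterion in Section 8 is a minimum for counting an event and does not escalate a long one.

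**The case against.** The best defence is that this is a deliberate trade-off. The masked review already adds a safeguard to usual care. More alerts could reduce hypoglycemia in the control arm, which is the primary endpoint and the quantity whose variance Section 9 wants from this pilot. These infants have already had two documented hypoglycemic episodes, and Section 4d expects routine glucose monitoring, so most will be sampled well within 12 hours. The 715-minute case is an edge case: a low that is still present at the next check is found and is no longer unrecognized. Sensor accuracy is itself under evaluation, so some long CGM lows may be false. All of this stands. It limits how often the gap would matter and gives the fix a cost, but it does not supply a duty to notify.

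Four stronger readings are tempting and should not be adopted.
- *Severe lows of about 3 hours are being missed.* The 3 hours in Section 2 is lead time of CGM over a scheduled blood test, for hypoglycemia in general. It is not the length of a never-recognized low below 40 mg/dL. The ratios it would give, 180 / 45 = 4.0 or 180 / 105 = 1.7, therefore have no support in the documents.
- *The rule ignores exposure many times greater than what it acts on.* The largest ratios hold only if the Section 8 floor does not apply to the alert, which is unstated.
- *A long low is never counted.* No daily reset is described, so it may count as the first of three. Two more unrecognized severe episodes would still be needed.
- *The team is barred from calling earlier.* Nothing forbids it, but nothing requires it.

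**Conclusion.** The point holds as a gap in a safety rule. The Standard of Care alert is triggered only by a count of three, and a single prolonged unrecognized low below 40 mg/dL requires no notification even when the daily review shows it. This rests on the text of Sections 4a and 4d and is the same under either reading of Section 8.

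Its frequency cannot be estimated, because the documents give no rate for such lows. Its duration is bounded at just under 12 hours if calibration keeps to schedule and the meter agrees with the sensor, and will usually be much shorter. The terms for an unrecognized episode are not defined specifically for the alert, but one unbroken low is one episode under any sensible definition. The point does not undermine the trial's comparison. It is a cheap improvement that is worth making.

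**What to change.** Keep the three-episode rule and add to Section 4a and to Section 4d (Interventions): *The study team will also alert the NICU providers immediately when the daily review shows any single continuous stretch of CGM <40 mg/dL longer than 1 hour with no blood glucose value obtained during it.* In the Section 4a sentence on changes to Standard of Care management, replace *repeated* with *repeated or prolonged* so that the three places agree.

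One hour is an assumption. A limit of 1 to 2 hours is a reasonable range for the sponsor and IRB to confirm. The choice matters for lows in between: the 115-minute example alerts at 1 hour and not at 2. A cumulative 24-hour limit is not needed. If one is wanted, it should cover unrecognized time only, since otherwise lows that the NICU already knows about would trigger redundant alerts. No sentence on the Section 8 floor or merge is needed either, because a single stretch of over an hour exceeds the floor and involves no merging.

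The change takes a short protocol amendment. The trace is already downloaded and reviewed daily, so no staff, device or procedure is added. Some control infants will have extra blood checks, including for false sensor lows. A blood value settles those, since care is based only on blood results. The contrast between arms narrows slightly and the variance estimate may be affected, by an amount that the documents do not allow to be quantified. With ten infants per arm and no power claim, that is an acceptable price.
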